6.3 PRIMARY SAFETY VARIABLE

Data will be analyzed according to the occurrence, at any time between tenecteplase administration and day 28, of intracranial hemorrhage or major bleeding event (defined above). Outcome will be the proportion of patients who have suffered no intracranial hemorrhage or major bleeding event. Those patients who have suffered an intracranial hemorrhage or major bleeding event will be assessed as failures for the purposes of the safety analysis.

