2.3 STUDY OUTCOMES

The following outcomes will be tracked for the trial:

Primary outcome is: the proportion of patients alive and free of respiratory failure (not requiring non-rebreather, high-flow nasal cannula, non-invasive positive pressure ventilation, or mechanical ventilation) at 28 days

- A. Primary safety outcome: Occurrence of intracranial bleeding or major bleeding (Definition: A bleeding episode leading to hemodynamic compromise requiring emergency intervention (such as replacement of fluid and/or blood products, inotropic support, or surgical treatment), or life-threatening or fatal bleeding) within 72 hours of randomization. All outcomes will be assessed in a blinded fashion by the DSMC/CEC.
- B. Secondary outcomes include: 14-day in-hospital mortality, 28-day mortality, ventilator-free days, respiratory failure-free days (not requiring NRB, HFNC, NIPPV, or mechanical ventilation), vasopressor-free days, vasopressor requirements at 24 and 72 hours, P/F ratio at 24 hours and 72 hours, ICU-free days, hospital length of stay, new renal failure, need for renal replacement therapy
- C. Mortality: given a high mortality rate amongst this patient population, patients who die will be included in statistical analysis. Variables of interest will be calculated until the point these patients expire.

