Given the positive results in the cardiac literature, tenecteplase has also been trialed for acute ischemic stroke; however, there has been limited adoption compared to alteplase following the NINDS trial in 1995.²⁷ Smaller phase II trials were performed throughout the 2010s, again suggesting equivalent efficacy regarding reperfusion with a similar safety profile between tenecteplase and alteplase. The first dose-escalation study was published in 2005 and assessed tenecteplase doses between 0.1 and 0.5 mg/kg.²⁸ Despite an increasing incidence of asymptomatic intracranial hemorrhage (ICH) between 0.1 and 0.4 mg/kg doses, no symptomatic ICH were seen. However, the 0.5 mg/kg tier was terminated prematurely given a high incidence

of symptomatic ICH (2 of 13 patients). Overall long-term functional outcomes were similar between the lower dose tenecteplase and historical controls treated with tPA.

The ATTEST trial randomized 104 patients with acute ischemic stroke to receive either TNK or tPA.²⁹ The primary endpoint of salvaged penumbra was identical between the two groups (68%), and rates of symptomatic intracranial hemorrhage were not statistically different (2% and 4% for TNK and tPA, respectively, $p=0.55$). Another randomized controlled trial published in 2012 assessed either alteplase infusion or dose-escalated tenecteplase (0.1 or 0.25 mg/kg) in patients with acute ischemic stroke less than 6 hours after symptom onset.³⁰ Patients treated with tenecteplase had better rates of radiographic reperfusion as well as short- and long-term clinical improvement, with higher doses (0.25 mg/kg) performing better than lower. Rates of intracranial and non-intracranial hemorrhages were consistent in all three groups.

Most recently the EXTEND-IA TNK trial assessed 202 patients randomized to either tenecteplase bolus (0.25 mg/kg) or alteplase prior to endovascular thrombectomy for large vessel occlusion.³¹ The primary outcome of angiographic reperfusion prior to thrombectomy (or absence of retrievable thrombus) was significantly greater in the TNK group, compared with tPA, present in 22% and 10%, respectively. Tenecteplase was also associated with improvement in 90-day functional outcomes, and similar rates of symptomatic intracranial hemorrhage.

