6. STATISTICAL CONSIDERATIONS

6.1 DETERMINATION OF SAMPLE SIZE

Assuming a total of 60 subjects enrolled with a 2:1 ratio in the tenecteplase:control arms and a good outcome rate of 15% in the control arm, this study has approximately 70% power to detect an absolute difference of 35% in the good outcome rate between the combined tenecteplase arms (40 patients) and the control arm (20 patients) and approximately 55% power to detect an absolute difference of 35% between each of the tenecteplase arms (20 patients) and the control arm (20 patients), at the 2-sided 0.05 significance level based on the Fisher's exact test. Good outcome rate is defined as the proportion of patients who are alive and free of respiratory failure at 28 days. If the true rate of symptomatic ICH or major bleeding requiring transfusion is 3%, the chance of observing at least one of these events in 20 patients is at least 45%. The chance of observing at least one event in 20 patients increases to at least 70% if the true event rate is 6%.

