Appendix 1: Study Flowchart

- a. Randomization will be done using an escalating-dose randomized design. It will be block randomization of 10:5 (treatment:control) performed twice per dose of TNK-tPA. If no safety triggers occur after 20 patients enrolled at the low dose, then the high dose enrollment will be undertaken with block randomization of 10:5.
- b. Vital signs include respiratory rate, pulse rate, systolic and diastolic blood pressure and temperature. Vitals are to be measured within 60 minutes prior to each tenecteplase infusion and, if clinically indicated, during or after the infusion.
- c. Labs to be collected include: CBC: Platelet, WBC, Hb, Hct; BMP: Na, K, Cl, HCO3, BUN, Cr; Glucose (finger stick or lab); LFT: ALT, AST, Bili, Alk Phos, LDH, Total Protein, Albumin, D-dimer, fibrinogen, CRP, ferritin, troponin-I; Coagulation: INR, aPTT, Anti-Xa, PT (only if the patient is taking an anticoagulant); Thromboelastograms
- d. Only coagulation labs need to be checked every 6 hours post randomization which includes: INR, aPTT, PT (only if the patient is taking an anticoagulant)
- e. Arterial blood gases to be collected include: Arterial Blood Gas: pH, pCO2, pO2, SaO2, Lactate
- f. Ventilator/Respirator Setting settings to be collected include: RR, TV, PEEP, Plateau Pressure; NIPPV settings (if appropriate): RR, IPAP, EPAP, FiO2; HFNC settings (if appropriate): FiO2, flow
- g. Neurological exams are to be performed every time room access is breached.
- h. For patients already on therapeutic heparin, continue heparin infusion. For patients not already on heparin or other anticoagulant, begin heparin with tenecteplase infusion starting with bolus dose of 60 Units/kg IV once, followed by 12 Units/kg/hr. For patients who were receiving enoxaparin at time of inclusion, tenecteplase infusion can be given immediately. Delay heparin to 12 hours after the most recent enoxaparin dose, beginning at an infusion rate of 18 Units/kg/hr. Do not administer a bolus dose of heparin and check PTT every 6 hours; adjust heparin to achieve target PTT of 70-90 seconds.
- i. All image collection should follow institution specific standard of care guidelines.

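### The primary safety outcome counts any intracranial haemorrhage over all patients with no scheduled post-dose head scan, so silent bleeds are under-ascertained and the event differs from the symptomatic one used in Sections 4.2 and 6.1

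*Combined protocol and SAP*

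**What the plan says.** **Event and denominator.** Section 2.3 names the primary safety outcome as "Occurrence of intracranial bleeding or major bleeding", "within 72 hours of randomization". Section 6.3 analyses events "at any time between tenecteplase administration and day 28" and reports patients without one as a proportion: "Outcome will be the proportion of patients who have suffered no intracranial hemorrhage or major bleeding event". On scoring it says: "Those patients who have suffered an intracranial hemorrhage or major bleeding event will be assessed as failures". Neither section limits ICH to symptomatic cases or the denominator to patients who were scanned.

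**Event used elsewhere.** The safety trigger in Section 4.2 uses symptomatic ICH or a major acute bleed. The precision statement in Section 6.1 also uses the symptomatic event: "If the true rate of symptomatic ICH or major bleeding requiring transfusion is 3" per cent, it says, the chance of at least one event in 20 patients is at least 45%. It gives at least 70% for a rate of 6%.

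**Imaging.** Footnote i of Appendix 1 reads "All image collection should follow institution specific standard of care guidelines". Sections 4.5.5 and 4.5.6 also list imaging as standard of care, and 4.5.6 collects it only if the patient is still admitted. The one head CT that the protocol requires (Section 4.1.1) comes before randomisation and applies to a subset. Section 4.5.4 requires serial neurological examinations after dosing but lists no imaging item.

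**Missing data.** The carry-forward rule stands under the efficacy variable in Section 6.2. Nothing says how to classify ICH status in a patient with no post-dose scan.

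**The concern.** A haemorrhage without symptoms is visible only on a scan. Section 6.3 counts such haemorrhages but schedules nothing to find them, and it fails only patients with an event. Absence of a scan is therefore treated as absence of a bleed. The plan does not say this outright, but 6.3 as written leaves no other category for an unscanned patient.

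Two things are at stake. First, the reported bleeding rate will be too low by an unknown amount, and in the reassuring direction, in a dose-escalation trial whose main product is a safety estimate. Secondly, the planning figures in 6.1 and the trigger in 4.2 concern a different event from the one in the headline analysis, so a reader cannot use the former to judge the latter.

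**Working it through.** **Step 1: reproduce the plan's figures.** P(at least one event in n patients) = 1 − (1 − p)^n, with n = 20 from Section 6.1.
- p = 3%: 1 − 0.97^20 = 45.6% (plan: at least 45%).
- p = 6%: 1 − 0.94^20 = 71.0% (plan: at least 70%).

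Both reproduce, for symptomatic ICH or major bleeding.

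**Step 2: inputs for the event in 6.3.**
- m, symptomatic ICH or major bleeding: 3% (Section 6.1).
- q, true silent-ICH rate: 5% (assumed; the documents give none).
- s, fraction with a post-dose head scan: 25% to 50% (assumed; the documents give none).
- Also assumed: scanning is independent of silent bleeding, every scan is timed to catch the bleed, symptomatic ICH and major bleeds are all found clinically, and m and q add.

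**Step 3: observed composite = m + q·s; true composite = m + q.**

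| Scanned | Composite seen | Under-count | P(≥1 in 20) |
|---|---|---|---|
| 25% | 3% + 5% × 0.25 = 4.25% | 3.75/8 = 47% | 1 − 0.9575^20 = 58% |
| 50% | 3% + 5% × 0.50 = 5.5% | 2.5/8 = 31% | 1 − 0.945^20 = 68% |
| 100% | 3% + 5% = 8% | 0 | 1 − 0.92^20 = 81% |

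Among 40 treated patients the expected number of missed silent bleeds is 40 × 3.75% = 1.5 at 25% scanned and 40 × 2.5% = 1.0 at 50%.

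**Step 4: wider range.** With m = 3% or 6%, q = 3% to 10% and s = 25% to 75%, the composite is under-counted by between 8% (m = 6%, q = 3%, s = 75%) and 58% (m = 3%, q = 10%, s = 25%).

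**Step 5: drop independence.** If silent bleeders are scanned r times as often as patients overall, the fraction of silent bleeds missed is 1 − s·r. At s = 50% this is 75%, 50% and 25% for r = 0.5, 1 and 1.5. A scan taken before the bleed would add to the loss.

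**Step 6: comparisons.** With equal scanning in both arms, the silent-ICH ratio is unchanged but the difference shrinks by the factor s: an assumed 10% against 2% shows 8 points at full scanning, 4 at 50% and 2 at 25%. With 50% scanned in one arm and 25% in the other, equal true rates would show as 5.5% against 4.25%, a ratio of about 1.3.

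**The case against.** The clinically important events are actively sought. Section 4.5.4 requires frequent GCS and NIHSS examinations, and Section 5.2.3 has any ICH reported within 24 hours, so silent cases that are found can already be listed. This stands, but examinations do not find silent bleeds and reporting reaches only those already found.

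Three stronger readings are tempting, and the documents do not support them.

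- *The under-count equals the unscanned fraction.* A reader might infer this. It applies to the silent component alone, and only if scanning is independent of bleeding and well timed (Step 5). In every case calculated, the composite loses less than the unscanned fraction.
- *The dose-dependent harm is the silent one.* A reader might infer this from Section 3.3.1 on a stroke dose-escalation study: "Despite an increasing incidence of asymptomatic intracranial hemorrhage (ICH) between 0.1 and 0.4 mg/kg doses, no symptomatic ICH were seen". The same paragraph goes on to report symptomatic ICH in 2 of 13 patients at 0.5 mg/kg, a tier that was stopped early, and 0.50 mg/kg is this trial's high dose. The section also reports a myocardial infarction study in which ICH did not depend on dose.
- *Arms will be scanned unequally.* Staff, investigators and subjects are blinded (4.2), events are adjudicated blind (2.3, 5.4.1), and each dose stage has concurrent placebo. Unequal scanning between arms, or between dose stages at up to six sites, remains possible but is not shown.

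Two objections to the remedy also stand. A rate among scanned patients is selected by indication, so it is not an unbiased estimate. And the documents do not define symptomatic ICH, which is hard to judge in sedated, ventilated patients.

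**Conclusion.** The concern holds in a limited form. As written, 6.3 counts any ICH over all patients, no post-dose head scan is scheduled, and unscanned patients are event-free by default. Silent ICH is therefore under-ascertained, towards apparent safety, and the analysed event is not the one in 4.2 and 6.1. The direction follows from the text; the size does not. On 6.1's 3%, with an assumed 5% silent rate and 25-50% scanned independently of bleeding, the composite reads 4.25-5.5% instead of 8%, and the chance of at least one event in 20 is 58-68% instead of 81%. Symptomatic ICH and major bleeding are not affected on these assumptions. This should be corrected, but it does not invalidate the trial.

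**What to change.** 1. In Sections 2.3 and 6.3, make the primary safety proportion symptomatic ICH or major bleeding over all dosed patients, matching the ICH wording in 4.2 and 6.1. State a definition of symptomatic ICH that the adjudication committee can apply to sedated patients.
2. In the same edit, reconcile the 72-hour window in 2.3 with the day-28 window in 6.3, since the window also decides which scans count.
3. Report any ICH and asymptomatic ICH separately, by arm and dose. For asymptomatic ICH, give the number found over the number with a post-dose head scan, show the number scanned, and label the row descriptive because scanned patients are selected.
4. State that unscanned patients are not scored as free of asymptomatic haemorrhage.

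The cost is a few sentences, one definition and one table, with no extra scans. Appendix 1 marks standard-of-care imaging in the first 72 hours but the list in 4.5.4 has no imaging item, so confirm that the case report form records whether a head scan was done. The downside is that the headline composite no longer includes silent bleeds, which appear in their own row.

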6.4 ONGOING SAFETY ANALYSIS

Should there occur, at any time during the study, a difference between the control and treatment cohorts of >2 intracerebral hemorrhages then the study will be halted. Per protocol, the DSMC/CEC will review all ICH's (SAE's). Following each of these individual case reviews (after analysis/interpretation locked), the DSMC/CEC statistician (who is unblinded, not the study statistician, who will remain blinded) will provide summary data on the ICH's according to cohort. If there is a greater than 2 ICH differential then the study will be halted. Additionally, the DSMC/CEC will be reviewing all enrollments, with summary statistics for each cohort (provided by the DSMC/CEC statistician) after each 15 patients are enrolled. They are empowered to halt study enrollment at each of these review points should there be safety concerns. After each of these planned DSMC/CEC reviews the DSMC/CEC will generate a formal report to provide to the study PI.

6.5 METHOD OF ANALYSIS

Continuous and categorical variables will be presented and summarized by using means with standard deviations and frequencies with percentages respectively. Tukey's method for pairwise comparison and large sample based multiple comparison of logits will be performed for continuous variables. Logistic regression modeling will be used for covariates adjustments and subgroup analyses. Survival functions will be estimated by applying Kaplan-Meier method. Statistical testing will be performed at two-sided 5% level of significance.

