1.5 STUDY RATIONALE AND BENEFIT-RISK ASSESSMENT

Based on a recent JAMA publication, intubated COVID-19 patients in NYC can expect a mortality rate as high as 88%.¹⁶ This dismal mortality rate has driven us to make clinical decisions regarding the use of off-label application of otherwise FDA approved medications in a hope to improve outcomes. Therefore, we undertook the off-label utilization of tenecteplase (at the lower EXTEND-IA TNK dosing) with concomitant heparin administration for the treatment of 5 refractory COVID-19 patients. We were highly encouraged by this experience in that all patients had improvement in oxygenation, alveolar ventilation, and hemodynamics within 24-48 hours. Four of the five patients had shock resolution, while the fifth patient had dramatic reductions in vasopressor requirements. No clinically significant bleeding was noted in any of these patients. As a result, we believe that a high-quality prospective Phase II, dose escalation trial is indicated.

To assess the efficacy of tenecteplase on critically ill patients with COVID-19 and hypoxic respiratory failure, we propose a multi-center, randomized, controlled, double-blind, dose-escalation trial comparing tenecteplase versus placebo. We intend to enroll 60 subjects: 40 randomized for intervention (20 each at doses of TNK, 0.25 mg/kg and 0.50 mg/kg) and 20 for placebo. Planned inclusion criteria are confirmed respiratory failure requiring mechanical ventilation for not greater than 48 hours, or non-rebreather (NRB), high-flow nasal cannula (HFNC), or non-invasive positive pressure ventilation (NIPPV) for less than 96 hours, with confirmed infection with SARS-CoV-2 virus (PCR positive within 14 days), elevated D-dimer (2 times upper limit of normal,¹⁷ and lack of stringent exclusion criteria. Primary efficacy outcome will be clinical status assessment at 28 days (proportion of patients alive and free of respiratory failure). Primary safety outcome will be rate of ICH or major acute hemorrhage (defined as bleeding episode leading to hemodynamic compromise requiring emergency intervention [such as replacement of fluid and/or blood products, inotropic support, or surgical treatment], or life-threatening or fatal bleeding). Secondary outcomes include survival, ventilator-free days, respiratory failure-free days, vasopressor-free days, improvement in PaO₂/FiO₂, and ICU and hospital length of stay.

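### Free-day and length-of-stay outcomes get only mean/SD and Tukey's method and are counted only until death, so patients who die can keep free days and, if many values are zero, the summary is poor and power can be lost

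*Combined protocol and SAP*

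**What the plan says.** Section 2.3 lists among the secondary outcomes "ventilator-free days, respiratory failure-free days (not requiring NRB, HFNC, NIPPV, or mechanical ventilation), vasopressor-free days", together with ICU-free days and hospital length of stay. It gives no counting window for any of them. On death it says only that patients who die stay in the analysis and that "Variables of interest will be calculated until the point these patients expire".

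Section 6.5 holds the whole analysis method. Its summary rule is "Continuous and categorical variables will be presented and summarized by using means with standard deviations and frequencies with percentages respectively". Its comparison rule is "Tukey's method for pairwise comparison and large sample based multiple comparison of logits will be performed for continuous variables". Testing is at the two-sided 5% level. No median, quartiles, share at zero, rank test or two-part method appears, and no separate rule is given for free days.

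Section 6.1 assumes "a good outcome rate of 15% in the control arm" and a 35-point absolute improvement on tenecteplase. Section 3.3 says the trial is not sized for significance and is meant to estimate a benefit signal for a phase III trial.

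**The concern.** Free days run from 0 to a ceiling and, in severe respiratory failure, tend to pile up at zero with the rest spread over the range. A mean and SD cannot show that shape. Tukey's method is built for roughly normal data with a common variance.

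The death rule adds a second problem. If counting simply stops at death, a patient who dies may carry forward free days, and an early death looks like a short stay. An outcome meant to combine survival and recovery could then favour the arm with more early deaths.

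At stake is the descriptive evidence for phase III from four free-day outcomes and hospital length of stay, and some efficiency in comparing arms.

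**Working it through.** **1. The plan's own figure.** Section 6.1 gives about 70% power (40 v 20) and 55% (20 v 20) for 15% v 50% by Fisher's exact test. With the continuity-corrected arcsine approximation, h = 2·asin√(p1 − 1/(2·n1)) − 2·asin√(p2 + 1/(2·n2)) and power = Φ(h/√(1/n1 + 1/n2) − 1.96):

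- 40 v 20: adjusted rates 0.4875 and 0.175; h = 0.683; 0.683/0.274 = 2.49; Φ(0.53) = 70.3%.
- 20 v 20: adjusted rates 0.475 and 0.175; h = 0.658; 0.658/0.316 = 2.08; Φ(0.12) = 54.8%.

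Both agree with the plan (exact enumeration gives 74.5% and 57.3%), so 15% and 50% are the design rates. They belong to the primary outcome. The plan gives no distribution or power for any free-day outcome, so everything below rests on stated assumptions.

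**2. How many zeros?** If every patient without a good outcome scored zero, the zero share would be 1 − 0.15 = 85% in control and 1 − 0.50 = 50% on tenecteplase. Overall that is (20 × 0.85 + 40 × 0.50)/60 = 37/60 = 61.7%. This proxy fits respiratory failure-free days best, because the primary outcome uses the same kinds of support.

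**3. What mean and SD would show.** Let a share p of patients have non-zero days, uniform on 1 to 28 (mean 14.5, mean square 275.5). Then mean = 14.5p and variance = 275.5p − (14.5p)².

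- Control, p = 0.15: mean 2.2; variance 41.3 − 4.7 = 36.6; SD 6.0; median 0.
- Tenecteplase, p = 0.50: mean 7.25; variance 137.75 − 52.56 = 85.2; SD 9.2.

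The control SD is about 2.8 times the mean (6.05/2.175) for a variable that cannot be negative, and the variance ratio is 85.2/36.6 = 2.3.

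**4. Power.** Three arms of 20, 4,000 simulated trials per scenario, one dose v control. Tukey uses the studentized range with 57 degrees of freedom, a per-pair level of about 0.019. The rank test (tie-corrected Mann-Whitney) is run at that same level.

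| Zero share, control to dose | Non-zero days | Tukey | Rank test |
|---|---|---|---|
| 85% to 50% | 1-28 | 31% | 48% |
| 85% to 50% | 1-14 | 33% | 48% |
| 85% to 50% | 14-28 | 48% | 49% |
| 70% to 40% | 1-28 | 21% | 29% |
| 60% to 40% | 1-28 | 9% | 12% |
| 30% to 15% | 1-28 | 6% | 6% |
| 50% to 50% | 1-20 to 9-28 | 14% | 7% |

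Further runs at 85% to 50%, 3,000 trials each, gave 31% v 50% (days 1-28) and 39% v 47% (28 minus a gamma-distributed time). The range at these zero shares is therefore about 31-48% for Tukey and 47-50% for the rank test. Under the null, Tukey's familywise error was 3.3% to 5.0%.

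**5. The death rule, by illustration.** Patient A never needs vasopressors and dies on day 12. Patient B needs them through day 20 and survives to day 28. Counting until death, A has up to 12 vasopressor-free days and B has 28 − 20 = 8, so the patient who died ranks higher. With deaths at zero, A has 0 and B has 8. In the same way, a death on day 3 gives a shorter hospital stay than a discharge home on day 12.

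**The case against.** The strongest reply is that little depends on this. The outcomes are secondary, section 3.3 disclaims significance, type I error holds, and a difference in mean free days is a meaningful quantity. All of that stands. It makes this a minor point, and it would be wrong to call the planned summary uninterpretable. But a trial meant to estimate a signal depends on good description, and section 6.5 still prespecifies testing.

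Three stronger readings are tempting and not supported.

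- **A reader might infer that most free-day values will be zero.** The 15% is status at day 28, not a count of days. Entry admits patients on high-flow, non-rebreather or non-invasive support, who can accrue many ventilator- and vasopressor-free days, and the 88% mortality in section 1.5 concerns intubated patients only. The plan does not score death as zero. Even on the proxy, tenecteplase arms reach only half.
- **A reader might infer that variances must differ if the drug works.** The ratio near 2 is specific to 15% v 50%. With 28 minus a gamma-distributed time for non-zero days, 30% v 85% non-zero gives a ratio of about 0.95 despite a large effect.
- **A reader might infer that Tukey always loses power.** The table shows ties, and a reversal (14% v 7%) when the effect lies only in the non-zero days.

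**Conclusion.** The concern holds in limited form. Section 6.5 gives free-day and length-of-stay outcomes only mean/SD and Tukey's method. Section 2.3 counts until death, with no window and no death score. That gap in definition is the firmest part, because it follows from the text without any simulation.

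The descriptive and power parts are conditional on death or continued support scoring zero. A large share of zeros is then likely, up to 85% of controls for respiratory failure-free days if every non-good outcome scores zero. At the assumed 85% v 50%, a rank test gains from about 1 to about 19 percentage points over Tukey for one dose v control. Elsewhere the gain shrinks to nil, or becomes a loss of about 7 points (14% v 7%) in the scenario with equal zero shares. The zero shares and day distributions are assumptions. The validity of the tests is not in question; this is a low-severity improvement in definition, description and efficiency.

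**What to change.** - **Section 2.3:** define each free-day outcome over a fixed 28-day window with deaths scored as zero free days, and reconcile this with the sentence on calculating variables until death. State how length of stay treats death so that an early death does not count as a favourable short stay.
- **Section 6.5, description:** for these outcomes report median, quartiles and percent zero alongside the mean.
- **Section 6.5, comparison:** prespecify a rank test, for example van Elteren stratified by dose stage for pooled tenecteplase v placebo, with a multiplicity-adjusted rank comparison for the three-arm pairwise tests so that familywise control is kept. The simulations used the unstratified rank test, so the stratified version's power was not checked.
- **Keep Tukey** for roughly normal variables such as the P/F ratio, and clarify the sentence that assigns a comparison of logits to continuous variables.

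The cost is protocol and SAP wording, with no extra patients. The downside is that the test no longer targets a mean difference in days, so the mean stays as a descriptive summary, and some power is given up if the effect lies only in the non-zero days.

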4.1.1 Inclusion Criteria

Patients must meet the following criteria for study entry:

- Patient/legally authorized representative has completed the Informed Consent Form
- Age ≥ 18 years
- Ability to comply with the study protocol, in the investigator's judgment
- Respiratory failure secondary to COVID-19 requiring mechanical ventilation for no greater than 48 hours, or high-flow nasal cannula (HFNC), non-rebreather (NRB) mask or non-invasive positive pressure ventilation (NIPPV) for less than 96 hours
- Confirmed infection with SARS-CoV-2 virus (PCR positive within 14 days)
- Elevated D-dimer (>2 times upper limit of normal within past 72 hours)
- For patient who are intubated >12 hours prior to randomization or with any evidence of neurologic deficit a head CT within 12 hours demonstrating no evidence of acute or subacute infarct or hemorrhage

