 - All women of childbearing potential will have a pregnancy test at screening. If a urine pregnancy test is positive, it must be confirmed by a serum pregnancy test.

- SARS-CoV-2 PCR Test**

A SARS-CoV-2 PCR Test will be conducted during screening to determine if the patient is COVID positive.

- Respiratory Status / Ventilator Settings**

Respiratory or Ventilator settings will be collected at Screening.

Tenecteplase–Icahn School of Medicine at Mount Sinai
Protocol ML42492

- Ventilator settings (if appropriate): RR, TV, PI (if PCV or PSV) FiO2, PEEP, Plateau Pressure
- NIPPV settings (if appropriate): RR, IPAP, EPAP, FiO2
- HFNC settings (if appropriate): FiO2, flow
- NRB settings (if appropriate): flow
- **Ordinal Scale Assessment**

The Ordinal Scale Assessment will be conducted daily to determine the patient's current status.

- **Imaging**

If the patient has a standard of care CT Scan or X-Ray performed, the imaging result will be captured in the Screening CRF.

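### Section 6.5 ties no baseline adjustment to the primary comparison, although the trial mixes intubated and non-intubated patients, records that status before randomisation and does not stratify on it

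*Combined protocol and SAP*

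**What the plan says.** Section 4.1.1 admits patients in respiratory failure "requiring mechanical ventilation for no greater than 48 hours, or high-flow nasal cannula (HFNC), non-rebreather (NRB) mask" or NIPPV. Section 4.5.2 states that "Respiratory or Ventilator settings will be collected at Screening", and section 4.5.3 lists respiratory status again among the pre-randomisation assessments. Sections 3.1 and 4.2 stratify randomisation by site and by nothing else.

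Section 6.2 defines the primary endpoint as a simple proportion at day 28. Section 6.1 gives power "at the 2-sided 0.05 significance level based on the Fisher's exact test", with "a good outcome rate of 15% in the control arm". It does so for the combined tenecteplase arms (40 v 20) and for each dose against all 20 controls. Section 6.5 does not name the test for the primary endpoint. On baseline variables it says only "Logistic regression modeling will be used for covariates adjustments and subgroup analyses". Intubation status is not named anywhere as a stratification factor or covariate.

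**The concern.** Baseline respiratory support is close to a baseline value of the outcome, and section 1.5 itself singles out intubated patients as having a very high mortality. With 20 controls, chance alone can leave the arms with quite different shares intubated. An unadjusted difference then mixes the treatment effect with that imbalance.

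Section 3.3 says the trial is meant to estimate a benefit signal for a phase III trial, so a distorted estimate harms its stated purpose. Because the covariates are left open, they could also be chosen after the outcomes are known.

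**Working it through.** **Inputs from the documents.** 40 tenecteplase and 20 control patients, control good-outcome rate 15%, target +35 points (so 50%), two-sided 0.05, Fisher's exact test (section 6.1). Mortality of intubated patients up to 88% (section 1.5), so at most 12% good outcomes at that extreme.

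**Assumptions.** The documents give neither the share intubated nor any outcome rate for non-intubated patients. I take half intubated, with 30% to 70% as a range, and these control rates (intubated / not intubated):
- 12%/18%: 0.5 × 12 + 0.5 × 18 = 15. This combines the protocol's own two figures.
- 5%/25%: 0.5 × 5 + 0.5 × 25 = 15. Stronger prognosis, still consistent with section 6.1.
- 5%/45%, average 25%, and 12%/60%, average 36%. Strong prognosis, but both averages exceed the 15% in section 6.1.

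**1. The plan's power.** Exact enumeration of both binomials, 15% v 50%:
- 40 v 20: 71.4% if the two-sided p-value is twice the one-tail value, 74.5% with the usual Fisher p-value. The plan says about 70%.
- 20 v 20: 57.3% either way. The plan says about 55%.

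The stated figures are reproduced closely, slightly on the cautious side.

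**2. Chance imbalance.** With independent binomial numbers intubated in each arm, the probability that the shares differ by at least 20 points is:

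| Share intubated | 40 v 20 | 20 v 20 |
|---|---|---|
| 50% | 17.1% | 26.8% |
| 30% or 70% | 13.5% | 22.6% |

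**3. Effect on the estimate.** Shift in the unadjusted difference = imbalance × outcome gap between strata. An imbalance of exactly 20 points gives 0.2 × gap. Among trials at or beyond 20 points, the same binomial calculation gives a mean imbalance of about 25 points, hence 0.25 × gap on average:

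| Rates | Gap | At 20 points | Average at 20 or more |
|---|---|---|---|
| 12%/18% | 6 | 1.2 | 1.5 |
| 5%/25% | 20 | 4 | 5 |
| 5%/45% | 40 | 8 | 10 |

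Against the 35-point target, the last column is 1.5/35 = 4%, 5/35 = 14% and 10/35 = 29%. In simulation the Mantel-Haenszel difference shifts by about zero, apart from small movements if the true risk difference itself varies between strata. With no treatment effect, the stratified test rejects in 4.4% to 4.8% of trials.

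**4. Effect on the Fisher test.** Take no treatment effect, with 17/40 v 13/20 intubated (42.5% v 65%, 22.5 points in favour of tenecteplase). The chance of a significant result favouring tenecteplase rises from 1.1% under balance to 3.3% (rates 5%/25%), or from 1.0% to 5.2% (rates 20%/60%). The nominal level is 2.5% per side.

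**5. Effect on power.** +35 points overall, common odds ratio, half intubated, unstratified to stratified:

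| Rates | 40 v 20, Fisher to exact stratified | 20 v 20, Fisher to exact stratified | 40 v 20, chi-square to CMH | 20 v 20, chi-square to CMH |
|---|---|---|---|---|
| 12%/18% | 74.6% to 75.0% | 57.4% to 60.0% | 79.1% to 79.2% | 69.4% to 67.2% |
| 5%/25% | 74.8% to 80.9% | 56.8% to 65.5% | 79.4% to 85.1% | 69.3% to 73.0% |
| 12%/60% | 69.3% to 80.5% | 46.8% to 64.9% | 75.6% to 85.1% | 59.2% to 72.1% |

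If intubation is not prognostic at all (15%/15%), the exact pair gives 74.8% to 74.4% (40 v 20) and 57.2% to 59.5% (20 v 20). The small 20 v 20 gain there owes nothing to prognosis. The chi-square pair loses about 3 points at 20 v 20. The effect model matters too: at 5%/25% with a constant +35 points in each stratum, chi-square to CMH at 20 v 20 is 69.4% to 69.3%, which is no gain.

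**6. Dose stage as a stratum.** Each stage has 20 treated patients and 10 controls (section 4.2). A per-dose comparison stratified by stage gets nothing from the other stage's 10 controls, because no patient in that stage received the dose. Thus 20 v 20 becomes 20 v 10. At 5%/25% with +35 points in each stratum, power falls from 69% unadjusted to about 47%.

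**The case against.** A reader might infer that the plan has decided to leave the primary comparison unadjusted. The text does not go that far: section 6.5 provides for covariate adjustment, and the Fisher test appears only as the basis of the power calculation. What can be shown is that nothing commits the primary comparison to any baseline variable.

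A reader might also infer a substantial loss of power. Under the protocol's own 12% and 15% figures the 40 v 20 comparison gains almost nothing, and CMH loses slightly at 20 v 20. Gains of 10 points or more need strong prognosis, which is assumed rather than documented. Section 3.3 also disclaims power for significance, so power is the weaker argument.

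Nor is an imbalance established. It is a risk of roughly one in six for the combined comparison, and in the two scenarios that match the 15% control rate the average shift is 5 points or less.

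All of this stands. It limits the size of the point but not its core, because the trial's stated aim is an estimate and the remedy needs no new data.

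**Conclusion.** The plan leaves the primary comparison uncommitted on an obvious baseline divide that it records and does not stratify on. The main consequence is a less reliable estimate. If half are intubated, about 17% of trials (40 v 20) or 27% (20 v 20) have an imbalance of 20 points or more, which moves the unadjusted difference by 1.5 to 10 points on average across the assumed rates. The 10-point figure needs a control rate above the plan's 15%. The change in power runs from a loss of about 3 points (20 v 20, weak prognosis) to gains of about 10 points or more (strong prognosis). The documents do not support a general claim that power is lost, or that adjustment has been ruled out. Confidence is medium, because the share intubated and the stratum rates are assumptions.

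**What to change.** State in section 6.5 that the primary analysis is a Mantel-Haenszel risk difference with a CMH or exact stratified test (say which), stratified by intubated yes/no at the pre-randomisation assessment. Keep the unadjusted Fisher test as a sensitivity analysis.

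Dose stage may be added as a stratum in the pooled 40 v 20 comparison only. In each per-dose 20 v 20 comparison use intubation alone, so that all 20 controls count. State also how site, the randomisation stratum, is handled.

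A single binary stratum is safer here than an open-ended logistic model, since only about 0.15 × 20 = 3 good outcomes are expected among controls.

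The cost is a few sentences and no new data. The downside is a slight loss of precision if intubation proves weakly prognostic.
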